3.7 Outcomes

- **Primary outcome:** Differences in EBL between cases and controls using clinical estimate versus device assessment.
- **Secondary outcomes: System performance (ROC sensitivity analysis and correlation).** Delta hemoglobin, transfusion requirements, administration of uterotonics, colloid resuscitation, post-partum hemorrhage or hemorrhagic shock.

4. Criteria for inclusion of subjects:

Pregnant women between the ages of 18-50.
Scheduled cesarean delivery.

5. Criteria for exclusion of subjects:

- Incarcerated patients
- Patient unwilling or unable to provide consent
- Intrauterine fetal demise (no fetal heart beat identified and documented by two physicians)
- Placenta previa or other known placental anomalies
- Enrolled in another trial that may affect outcome.

6. Sources of research material: Electronic medical records.

7. Recruitment methods and consenting process: See 3.1 above.

8. Potential risks

8.1 Loss of confidentiality: Any time information is collected, there is a potential risk for loss of confidentiality. Every effort will be made to keep the subject's information confidential; however, this cannot be guaranteed.

9. Potential benefits: With this novel approach of assessing blood loss more objectively during cesarean section, there are many potential benefits,

including: decrease in the delay in diagnosis of hemorrhagic shock, decrease in delay in interventions and improved postpartum surveillance. In addition, this data will be useful in designing a level 1 trial to measure outcomes such as transfusion rates, transfusion complications, hemorrhage and maternal death.

10. Data monitoring: The PI, research coordinator, and collaborators will ensure that all aspects of data quality adhere to the study design. This will include monitoring for adherence to consent procedures, inclusion and exclusion criteria, valid abstraction, correct entry, timeliness and responsiveness to data queries. Data will be collected and stored with the participant ID code only. The master enrollment log linking patient identifiers with study ID numbers will be kept in a password protected database on the Ob/Gyn department's internal server. Several data collection forms will be used. Data on these forms will be devoid of personal identifiers and will be securely stored at the division offices. The research coordinator will be available to monitor the data and correct any discrepancies based on source documents if needed.

11. Procedures to maintain confidentiality: Each subject will be assigned a study number with personally identifiable information deleted or removed. If needed, charts will be reviewed in the medical records area. Subjects' information will be de-identified and tagged with a number. Data will be collected and stored on a UTMB password-protected computer.

Statistical approach: We will be performing a prospective study. After defining cases and controls using the cutoff of upper quartile for pre- to postop- hemoglobin drop. We will use univariable and multivariable analysis to check for association between both blood loss assessment techniques using the device and the subjective clinical assessment among our cases and controls. We will be comparing cases versus controls (two groups) and EBL (continuous variable and primary outcome) hence t tests/means were used for our sample calculation; For the purpose of the study, we believe a sample size of 220 will be able to evaluate our primary outcome. Accounting for 10% loss of data or follow-up: **N total is 242 subjects**. This was based on a study of 50 patients having cesarean deliveries using the Triton System (the mean measured blood loss was 555.8 ml with a standard deviation of 317 ml (11). For a power of 80% and alpha of 0.05 and 25% effect size 1: 3 allocation (25%ile versus 75%ile PP delta hemoglobin):

Estimated sample sizes for a two-sample means test
t test assuming $sd_1 = sd_2 = sd$
 $H_0: \mu_2 = \mu_1$ versus $H_a: \mu_2 \neq \mu_1$

Study parameters:

alpha = 0.0500
power = 0.8000
delta = -139.0000
m1 = 555.0000
m2 = 416.0000
sd = 317.0000
N2/N1 = 3.0000

Estimated sample sizes:

N = 220
N1 = 55
N2 = 165

We will also be using multiple model correlation (Pearson correlation coefficient) (secondary outcome) between EBL Device and EBL Standard. We will also perform ROC curve analysis (secondary outcome) to compare the area under the curve (AUC) to predict Δ Hgb in the upper quartile by clinical estimate versus device assessment. The coefficient of multiple correlation takes values between 0 and 1; a higher value indicates a better predictability of the dependent variable (EBL Device) from the independent variable (EBL standard).

REFERENCES

1. AbouZahr, C. (2003). Global burden of maternal death and disability. *Br Med Bull*, 67, 1-11.
2. Chesley, L. C. (1972). Plasma and red cell volumes during pregnancy. *Am J Obstet Gynecol*, 112(3), 440-450.

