The University of Texas Medical Branch Galveston
Research Protocol

**Validating a New Method to Assess Estimated Blood Loss in the Obstetric
Population**

Principal Investigators: [name]
Co-Investigator: [name]
Faculty Sponsor: [name].
Funding: Department of Maternal Fetal Medicine

NCT03404375

1. Introduction/Background/Purpose:

According to the World Health Organization, postpartum hemorrhage (PPH) is the leading cause of maternal mortality in low-income countries and the primary cause of nearly one quarter of all maternal deaths globally (1). An estimated blood loss (EBL) in excess of 500 mL following a vaginal birth or a loss of greater than 1,000 mL following cesarean birth often have been used for the definition of postpartum hemorrhage, but the average volume of blood lost at delivery can approach these amounts when actually measured rather than estimated (2). More than half of all maternal deaths occur within 24 hours of delivery, most commonly from excessive bleeding (3). Worldwide, 140,000 women succumb to postpartum hemorrhage each year. The most common antecedents to postpartum hemorrhage are uterine atony, placental disorders, and trauma during delivery. Improving maternal health worldwide is one of the WHO's 8 Millennium Developmental Goals. The prevention and treatment of PPH is an essential step towards the achievement of that goal (4).

Estimates of blood loss at delivery are notoriously inaccurate, with under-estimation more common than over-estimation (5). Traditionally, the surgeon performing the cesarean section would estimate the blood loss by visually assessing the blood collected in the surgical drape and counting the number of lap sponges used thru out the procedure. Current detection and management of hemorrhage is heavily based on clinical judgment, which often leads to delay in recognition and intervention. Often, interventions such as fluid resuscitation and blood transfusion are not initiated until significant hemorrhage has already taken place. The traditional method for estimating blood loss is based on the surgeon and surgical staff's subjective assessment that is severely limited by human error and the presence of large volumes of amniotic fluid, irrigation, or both (6). Another limitation is that blood loss is frequently estimated at the end of the procedure.

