This study will be a prospective cohort study, in which we will evaluate two methods of evaluating intraoperative blood loss during cesarean delivery (usual clinical assessment versus Device). Of note, the subjects consented will be used as self-controls.

- 2. Summary of project:** This study will be a prospective cohort study. Patients who are scheduled for an elective cesarean and meet criteria for inclusion in the study will be approached for participation at same day of admission. Written informed consent will be obtained from the patients by the Co-PI ([name]) and by the study collaborators ([name],

[name], [name], [name], and [name]). If patients agree to participate, a CBC (complete blood count) will be obtained via venous puncture. The device will be used during the delivery in the operating room. The device will be used to assess EBL by the research staff only and results/ EBL assessment will be masked to the clinical team. Unmasking will only occur after collecting the data from the device with purpose to perform data analysis. Patient management will be according to the clinical team. All patients undergo a CBC postpartum. The drop in Hgb (Δ Hgb) between the pre and post cesarean CBCs will be calculated for each patient. Patients will be divided into quartiles of Δ Hgb. Cases will be those patients whose Δ Hgb is in the upper quartile, while controls will be those patients whose Δ Hgb is in the lower 3 quartiles. We will be comparing EBL by standard clinical assessment versus result from the device between cases and controls.

The colorimetric Triton system which comprises of the device, software analysis and staff training will be supplied by the manufacturer free of charge. We will be offering our skills, fellows and residents, who will be collecting data and we will be performing the data analysis. Results will be available to the manufacturer after results are completed. The results of this study will be presented in conferences or published in a peer-review journal.

Demographic information will be obtained from the electronic medical record. The data will be kept on a password secured UTMB computer. An encrypted USB flash drive will be used to transfer data. The data will be identified and linked to the patient using the medical record number (MRN). During data analysis, all patient identifiers will be deleted.

3. Study procedures: VISIT#1

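### ΔHgb defines the groups and is also a listed outcome, yet the plan never uses it as a continuous reference for the two blood-loss methods

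*Combined protocol and SAP*

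**What the plan says.** Section 2 (Summary of project) defines the variable: "The drop in Hgb (Δ Hgb) between the pre and post cesarean CBCs will be calculated for each patient". It then uses that variable to form the groups, with controls drawn from the other three quartiles: "Cases will be those patients whose Δ Hgb is in the upper quartile, while controls will be those patients whose Δ Hgb is in the" … The Statistical approach repeats the upper-quartile cutoff.

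Section 3.7 gives the primary outcome as "Differences in EBL between cases and controls using clinical estimate versus device assessment". Besides system performance (ROC and correlation), the secondary outcomes are "Delta hemoglobin, transfusion requirements, administration of uterotonics, colloid resuscitation, post-partum hemorrhage or hemorrhagic shock". No second definition or time point separates this delta hemoglobin from the grouping variable.

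For the secondary outcomes, the Statistical approach describes two analyses only:
- a Pearson (multiple) correlation between device EBL and standard EBL, with the device as the dependent variable;
- an ROC analysis comparing areas under the curve "to predict Δ Hgb in the upper quartile by clinical estimate versus device assessment".

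It does not say how delta hemoglobin or the other clinical outcomes will be analysed.

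**The concern.** One variable has two roles. Cases and controls are the only groups in the protocol, so an analyst working from Section 3.7 could well tabulate and test ΔHgb across them. The result would be an extreme p-value that says nothing about the device or the clinical estimate, but could be read as supporting the grouping or the device.

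The larger issue is what the plan leaves out. ΔHgb is the only yardstick external to both methods that the plan uses to judge them, and it is measured as a continuous quantity. The plan uses it only as upper quartile or not. The one correlation it specifies is between the two methods. That coefficient is symmetric, so it shows how far they move together and not which one follows the hemoglobin drop more closely. The aim is to validate the device against usual assessment, so the head-to-head question rests on a reduced form of the reference.

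**Working it through.** **Group sizes (Statistical approach).** Inputs: difference 139 mL, SD 317 mL, two-sided alpha 0.05, power 80%, ratio 1:3.

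n1 = (1 + 1/3) × (1.960 + 0.842)² × (317/139)² = 1.333 × 7.849 × 5.201 = 54.4, rounded up to 55. Then n2 = 165 and N = 220, as stated. The noncentral t gives n1 = 54.9, hence the same 55 and 165. The sample size is not in dispute; 55 and 165 are used below.

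**ΔHgb compared between groups cut on ΔHgb.** Assume a normal ΔHgb, in SD units. The upper-quartile cut is at z = 0.6745, where the density is 0.3178.
- Case mean = 0.3178/0.25 = 1.271.
- Control mean = −0.3178/0.75 = −0.424.
- Gap = 1.271 + 0.424 = 1.69 SD.
- Case variance = 1 + 0.6745 × 1.271 − 1.271² = 0.242 (SD 0.49).
- Control variance = 1 − 0.6745 × 0.424 − 0.424² = 0.535 (SD 0.73).
- Pooled SD = √[(54 × 0.242 + 164 × 0.535)/218] = 0.680.
- t = 1.695/[0.680 × √(1/55 + 1/165)] = 1.695/(0.680 × 0.1557) = 16.0, p about 1.1 × 10⁻³⁸.

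In 4,000 simulated trials of 220 women with EBL unrelated to ΔHgb, this test was significant every time (largest p about 10⁻²⁹). Normality sets the size of the gap but not its existence: under any distribution, no control has a larger drop than any case.

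**What the quartile split keeps.** Under bivariate normality and weak to moderate correlation, the share of information kept is 0.3178²/(0.25 × 0.75) = 0.1010/0.1875 = 0.54. For this purpose, 220 women count as about 0.54 × 220 = 119.

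**What the planned correlation can show.** Suppose the methods correlate 0.4 with each other. That value fits device 0.5 and clinical 0.3 with ΔHgb, and fits the reverse equally well. It cannot tell the two cases apart.

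**Power at N = 220.** The documents give no correlations, so the values below are assumptions, with all three variables multivariate normal. The first test compares the two dependent correlations with continuous ΔHgb. The second compares paired AUCs for upper-quartile ΔHgb. Each row is 3,000 simulated trials at two-sided 5%.

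| Correlation with ΔHgb, better / worse method | Between methods | Correlation test | AUC test |
|---|---|---|---|
| 0.5 / 0.3 | 0.4 | 86% | 55% |
| 0.5 / 0.3 | 0.2 | 76% | 42% |
| 0.5 / 0.3 | 0.6 | 96% | 71% |
| 0.4 / 0.2 | 0.4 | 81% | 52% |
| 0.5 / 0.4 | 0.4 | 36% | 19% |
| 0.3 / 0.3 (no difference) | 0.4 | 5% | 5% |

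A separate simulation of the first row gave about 85% and 53%. The advantage holds across the range, and both tests keep the 5% level when the methods are equal.

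**The case against.** **No test of ΔHgb is stated.** The between-group comparison that the protocol names is of EBL. ΔHgb may be listed simply because every patient has it and it supplies the ROC target. This stands: the t of 16 belongs to a test that might be run, not to one that is planned. It supports a clarifying label and nothing stronger.

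**ΔHgb is already the common reference.** The AUC comparison judges both methods against it, so the plan does have a head-to-head analysis. This also stands, and the AUC comparison should stay. Only the continuous form is missing. The reply is that this form uses the reference more fully and needs no further data.

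**A stronger reading about hemorrhage.** A reader might infer that post-partum hemorrhage is circular too, or that it favours the clinical estimate by definition, because the Introduction mentions "a loss of greater than 1,000 mL following cesarean birth often have been used for the definition of postpartum hemorrhage". The documents do not support this.
- The groups are cut on ΔHgb, not on EBL. In the 4,000 trials above, EBL was lognormal with the protocol's mean of 555.8 mL and SD of 317 mL. A case-control test of EBL above 1,000 mL rejected in 4.1% (Fisher) to 5.6% (chi-square), close to the nominal 5%.
- The threshold is background. The study does not adopt it as an endpoint definition.
- Hemorrhage is not the yardstick for either method; the ROC target is upper-quartile ΔHgb.
- The device result is masked to the clinical team, so a charted diagnosis could reflect clinical EBL. That is an inference, and it would matter only if the diagnosis were used to judge the methods.

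What remains is that hemorrhage has no operational definition and no named EBL source. That is missing detail, not bias.

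**Conclusion.** The point holds in two limited parts. First, ΔHgb cannot serve as an outcome compared between groups that it defines. Such a comparison would show a gap of about 1.69 SD under normality, regardless of either method. As the protocol does not state the comparison, this is a matter of labelling.

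Second, the plan uses its reference only after a split that keeps about 54% of the information, and its one correlation cannot rank the methods. Under the assumed 0.5, 0.3 and 0.4, adding the continuous analysis raises power for the head-to-head question from about 53% to about 85%. The gain depends on those assumptions: when the methods differ little (0.5 versus 0.4), both tests are weak.

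The added analysis shows which method tracks ΔHgb more closely. It does not measure bias in mL, and it shares any weakness of ΔHgb as a reference with the planned AUC comparison. The primary outcome and the sample size are unaffected, so this is a worthwhile improvement and not a serious flaw.

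**What to change.** - In Section 3.7, label ΔHgb as descriptive or as the reference variable, and state that it will not be tested between cases and controls.
- In the Statistical approach, keep the AUC comparison. Add the correlation of each method's EBL with continuous ΔHgb, with confidence intervals, and a test of the difference between these two dependent correlations. Steiger's test would serve, or a bootstrap over patients if EBL is skewed.
- Describe the device-versus-clinical correlation as a measure of association between the methods, not as evidence of which is better.

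The cost is a change of wording and one more secondary analysis, which should be specified before the device data are unmasked. All three variables are already collected on each patient.

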3.1 Screening, Recruitment and Consenting: When a patient meets inclusion criteria for participation in our study, the obstetrical team will contact the research team. Written informed consent will be obtained from the patient by the PI, study coordinator, or collaborator. Study participation will be complete when the patient is discharged from the hospital. The data collected will be kept on a password secured UTMB computer. An encrypted USB flash drive will be used to transfer data. The data will be linked via MRN, which is needed to access the demographic data and will be deleted when the data is analyzed. Our target sample size is 242 subjects.

3.2. Baseline procedures: In some patients, there will be no baseline procedures aside from using the masked device for assessment of EBL. If a preop CBC is not indicated clinically or not available, then a preop CBC will be obtained after consent is signed. Funding from the Ob/Gyn department will cover the cost of this test. The device will be set by the manufacturer not

to reveal the EBL in order to mask the surgical staff hence not affecting the standard assessment of EBL already implemented in our surgical suite. Neither the subject's insurance nor the subject will be responsible for any charges relating to tests done only for research. Please see attached budget and departmental letter of support.

3.3. Study visits/Follow-up: One study visit will be needed during the trial. The subject participation will be considered complete when the subject is discharged home.

3.6. Withdrawals: Subjects who withdraw from the study after inclusion will be excluded from further follow-up. Data collected until the time of withdrawal will be analyzed.

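### Is the enrolment target of 242 too small for the 10% loss it is meant to cover?

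*Combined protocol and SAP*

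**What the plan says.** The Statistical approach section sizes the study with a two-sided comparison of mean estimated blood loss between cases (upper quartile of hemoglobin drop) and controls (the other three quartiles). The program output reproduced there is headed "Estimated sample sizes for a two-sample means test". It takes means of 555 and 416 mL ("delta = -139.0000"), a common SD of 317 mL, alpha 0.05, power 0.80 and three controls per case, and returns 55 + 165 = 220.

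The accompanying text states that "we believe a sample size of 220 will be able to evaluate our primary outcome", and then moves to the enrolment figure: "Accounting for 10% loss of data or follow-up", "N total is 242 subjects". Section 3.1 repeats it: "Our target sample size is 242 subjects". Neither place shows the inflation formula or says whether the 10% is counted on the 220 required or on the women enrolled.

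Two other passages bear on the point. Section 3.6 says of women who withdraw: "Data collected until the time of withdrawal will be analyzed". Section 2 defines cases and controls by the change between the pre- and post-cesarean blood counts ("Patients will be divided into quartiles of" that change), so a woman needs both hemoglobin values to be placed in a group.

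**The concern.** Attrition is normally expressed as a share of those who enter a study, and on that convention the analysable number is divided by one minus the loss rate. Multiplying by one plus the rate is a familiar shortcut that always gives a slightly smaller figure. Here it gives 242 where division gives 245. If 10% of the 242 enrolled women are lost, fewer than 220 remain. Because 220 is the smallest 1:3 design that reaches 80% power, any shortfall takes nominal power below the level the plan states. At stake would be an enrolment target, stated in two places, that does not deliver the power claimed for it at the loss rate written beside it.

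**Working it through.** **Inputs, all from the Statistical approach section:** difference 139 mL (555 − 416), SD 317 mL, two-sided alpha 0.05, power 0.80, three controls per case, 220 analysable, 10% loss, 242 in total. The SD is taken from a cited study of 50 patients.

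**1. Reproduce the 220.** For group sizes n1 and n2, power comes from the noncentral t distribution with n1 + n2 − 2 degrees of freedom and noncentrality (139 / 317) / √(1/n1 + 1/n2).

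- 55/165 (220 women): noncentrality 2.816, power 80.06%.
- 54/162 (216 women): power 79.3%.

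The plan's 220 is confirmed, and it is the minimum at 1:3.

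**2. Reproduce the 242.**

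- 220 × (1 + 0.10) = 242.0, an exact match.
- 220 / (1 − 0.10) = 244.4, so 245, which does not match.

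The plan therefore added 10% of the required number: 0.10 × 220 = 22 women. As a share of those enrolled, that allowance is 22 / 242 = 9.09%.

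**3. Apply the less favourable reading.** A loss of 10% of those enrolled is 0.10 × 242 = 24.2 women, leaving 217.8, that is 217 or 218. This is 2 to 3 below 220. The upper quartile would hold 217/4 = 54.25 or 218/4 = 54.5 women, so 54 or 55 cases.

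| Cases / controls | Total | Power |
|---|---|---|
| 55 / 165 | 220 | 80.06% |
| 55 / 163 | 218 | 79.94% |
| 55 / 162 | 217 | 79.88% |
| 54 / 164 | 218 | 79.46% |
| 54 / 163 | 217 | 79.39% |

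The fall runs from 80.06 − 79.94 = 0.12 to 80.06 − 79.39 = 0.67 percentage points. In terms of detectable effect, 80% power is reached at 140.1 mL with 54/163 and at 139.1 mL with 55/163, against the planned 139 mL.

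**4. Compare with the uncertainty already in the calculation.** Assuming normal data, the 95% interval for an SD of 317 mL estimated from 50 patients is 317 × √(49/χ²), with χ² quantiles 70.22 and 31.55 on 49 degrees of freedom. This gives about 265 to 395 mL. At the full 55/165 and a 139 mL difference:

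- SD 265: power about 92%.
- SD 395: power about 61%.

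That is a span of about 30 points, against at most 0.7 from the choice of denominator. Even a 3 mL change in the SD, to 320, gives 79.3% at 220 women, which is the size of the worst case in step 3.

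**The case for a change.** The best case for acting is that women are lost from those enrolled, so a share of those enrolled is the natural meaning of a loss rate. On that meaning 242 covers 9.1%, not 10%, and since 220 has no spare margin, power does drop below 80%. Section 3.6 does not rescue the figure: data kept up to withdrawal cannot place a woman in a group if a hemoglobin value is missing, nor compare the two methods if the device reading is missing. One sentence would make the target and the loss rate agree.

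The arithmetic in this argument is right, and so is the point about section 3.6. Division is also the better convention when the loss is a share of those enrolled. What does not stand is the step from there to an error. The plan never says that its 10% is a share of those enrolled, and its own figures fit the other base exactly, so there is no internal contradiction. The 10% is itself a round planning allowance, offered without supporting data, for a study with a single visit that ends at discharge and in which every patient has a postpartum blood count. The gap between 9.1% and 10% is finer than that allowance can bear. Those who want the wording settled would still keep 242 and leave every analysis as it is.

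**Conclusion.** The concern does not call for a change. The plan leaves the denominator of its 10% unstated; it does not miscalculate. If the allowance is 10% of the 220 required, 242 is exact. If it is 10% of those enrolled, the target is three women below 245 (3 / 242 = 1.2%), and a loss at that rate leaves 217 or 218 analysable women with power of 79.4% to 79.9% instead of 80.06%.

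These power figures take the plan's inputs as given: a 139 mL difference, a common SD of 317 mL, two-sided alpha 0.05, and a quartile split giving 54 or 55 cases. The comparison with SD uncertainty also assumes normally distributed blood loss in the 50-patient source study. On those assumptions the worst case is 0.7 points of power, far inside the imprecision of the planning SD. Rewording the sentence would record which base was used and nothing more: enrolment, the primary comparison and the conclusions that can be drawn would all be the same.

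### Does leaving the primary EBL test unnamed, with an equal-SD t test used for sizing, put the case–control result at risk?

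*Combined protocol and SAP*

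**What the plan says.** Section 3.7 (Outcomes) gives the primary outcome as "Differences in EBL between cases and controls using clinical estimate versus device assessment". Section 2 (Summary of project) defines the groups: "Cases will be those patients whose Δ Hgb is in the upper quartile", with the lower three quartiles as controls.

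For the analysis, the Statistical approach says "We will use univariable and multivariable analysis to check for association between both blood loss assessment techniques" and names no test, model or interval for the case–control difference. The t test enters in one place only, as a sizing device: "hence t tests/means were used for our sample calculation". The printed sample-size output carries the line "t test assuming $sd_1 = sd_2 = sd" and uses SD 317 mL in both groups, means of 555 and 416 mL, "delta = -139.0000", two-sided alpha 0.05, power 0.80 and a 1:3 split, giving 55 + 165 = 220. The SD comes from a published series of 50 cesarean deliveries: "the mean measured blood loss was 555.8 ml with a standard deviation of 317 ml". Pearson correlation and ROC analysis are named, but as secondary analyses.

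**The concern.** With no other test in view, an analyst might carry the equal-SD t test from the sizing into the analysis, and there are reasons to doubt equal SDs. Blood loss cannot be negative, yet a normal distribution with mean 555.8 and SD 317 puts P(Z < −555.8/317) = P(Z < −1.75) = 4.0% of women below zero. EBL is therefore probably right-skewed, with an SD that tends to rise with the mean.

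Cases are selected for a large hemoglobin drop, and the sizing gives them the higher mean. By design they are also the smaller group. A larger SD in the smaller group is the configuration in which a pooled standard error is too small.

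At stake would be a confidence interval for the mL difference that is too narrow, in a study meant to support a later multicenter proposal. If Welch were used instead, power would fall below the stated 80%.

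**Working it through.** **1. The plan's own figure.** Inputs from the sample-size output: difference 139, SD 317, ratio 1:3, alpha 0.05 two-sided, power 0.80.

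n(cases) = (1.960 + 0.842)² × (317/139)² × (1 + 1/3) = 7.849 × 5.201 × 1.333 = 54.4, so 55 cases and 165 controls, N = 220. Noncentral-t power is 0.8006 at 55/165 and 0.793 at 54/162. The stated N is exact under its assumptions.

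**2. Pooled interval with unequal SDs.** Let r = SD(cases)/SD(controls). The documents give no r. Two values follow from the planned means: 555/416 = 1.334 if SD is proportional to the mean, and √1.334 = 1.155 if variance is proportional to the mean. In units of the control variance:

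- pooled variance of the difference = [(54r² + 164)/218] × (1/55 + 1/165)
- true variance = r²/55 + 1/165
- coverage ≈ 2Φ(1.971 × √(pooled/true)) − 1

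For r = 1.334, r² = 1.780. Pooled = 1.1932 × 0.02424 = 0.02893 and true = 0.03236 + 0.00606 = 0.03842. The SE ratio is √0.753 = 0.868, and coverage is 91.3%.

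| r | pooled SE / true SE | coverage |
|---|---|---|
| 1.00 | 1.00 | 95% |
| 1.16 | 0.93 | 93.3% |
| 1.25 | 0.90 | 92.2% |
| 1.334 | 0.87 | 91.3% |

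**3. Simulation at 55/165 and a true difference of about 139 mL.** The first two rows draw EBL with overall mean 555.8 and SD 317, correlate it with hemoglobin drop, and take the top quarter by drop as cases. The others draw the groups independently at means 555 and 416 with the overall within-group SD held at 317.

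| Model | r | Coverage pooled / Welch | Power pooled / Welch |
|---|---|---|---|
| Log-normal, quartile selection | 1.25 | 92.3% / 94.5% | 79% / 75% |
| Gamma, quartile selection | 1.16 | 93.0% / 94.7% | 80% / 76.5% |
| Log-normal, constant CV | 1.33 | 91.3% / 94.1% | 78% / 72% |
| Normal | 1.16 | 93.1% / 95.0% | 78% / 73% |
| Normal | 1.33 | 91.1% / 95.0% | 77% / 68% |

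In the log-normal quartile-selection run, a t test on log EBL had 83.6% power. Mean half-widths there were 95 mL pooled and 107 mL Welch; in the gamma run they were 95 and 103 mL.

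**4. Type I error.** If EBL is unrelated to hemoglobin drop, splitting on the drop gives two groups with the same EBL distribution and hence equal SDs. Simulated pooled type I error is 4.8% (log-normal) and 5.0% (gamma).

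**5. Comparison with the uncertainty in the SD.** Under normal theory, an SD of 317 from 50 women has a 95% interval of 317 × √(49/70.2) = 265 to 317 × √(49/31.6) = 395 mL. With √(1/55 + 1/165) = 0.1557, the standardised difference is 139/(265 × 0.1557) = 3.37 or 139/(395 × 0.1557) = 2.26. Power of the planned test then runs from about 92% to 61%. The gap between pooled and Welch is small beside that.

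**The case for a change.** The best case for a change has three parts:

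- The document shows one test for this comparison, so an analyst would most naturally reuse it.
- The SD ratios are not arbitrary. They come from the plan's own means, or from its own mean and SD combined with its quartile rule.
- Naming Welch takes one line, costs almost nothing when SDs are equal (half-width 96.9 against 96.8 mL), and removes an analyst's choice worth about 3–6 power points.

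Some of this stands. The univariable test is unnamed, and if an interval in mL is reported, Welch has the better coverage whenever cases vary more.

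The claim of harm does not stand. It needs three things the documents do not supply: a decision to pool, a reported confidence interval, and an SD ratio well above 1. The text ties the t test to sizing, and the only inferential statement is a two-sided test of equal means. That test keeps close to its stated error rate and power under the skewed models used to argue against it.

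Nor is Welch the only answer. If right skew is the premise, log EBL or a rank test is equally defensible, and log EBL had more power in the run above. Restating power at 75–76%, or asking for 240–248 evaluable women, reflects only the quartile-selection models. The constant-CV case gives 72% and needs about 260. Normal data give about 73% down to 67–68% and need about 260 to 296. One assumption-driven figure would replace another.

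**Conclusion.** No change to the plan follows. The omission is real: no univariable test is named for the primary EBL difference. But it is a gap that analysts fill sensibly once they see the group SDs and the shape of the data, and the choice between pooled and Welch is partly a trade-off.

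If a pooled interval were reported and cases had an SD 1.16–1.33 times that of controls, coverage would be about 91–93% instead of 95%. Type I error with no association would stay at about 5%, and pooled power would be 77–80% across all the models run. Welch brings coverage to about 94–95%, at a cost of about 3–6 power points under the skewed models and 5–9 for normal data, with no gain in type I error.

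These sizes rest on assumed SD ratios and distributions. The sizing at N = 220 is correct as it stands.
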